#### **8.3.2 Randomization code breaking during the study**

In case of an AE, the randomization code should only be broken in circumstances when knowledge of the IMP is required for treating the patient.

Code breaking can be performed at any time by using the proper module of the IRT and/or by calling any other phone number provided by the Sponsor for that purpose. Code breaking can be performed by a local study Investigator, sponsor physician or healthcare professional with direct responsibility for patient care. If the blind is broken, the Investigator should document the date, time of day, and reason for code breaking. The identity of the unblinded personnel, how the code was broken, and the treatment kit number should also be recorded. The Sponsor should also be informed. If the code is broken by the Investigator (or other medical doctor in emergency situation); the patient must be withdrawn from IMP administration.

Randomization code breaking will also be performed during the analysis of the Pharmacokinetic plasma concentration samples. Only the Project manager and lead scientist at the Bioanalytical laboratory will have access to the randomization code to allow for the sorting of the sotagliflozin plasma samples. The Bioanalytical lab and responsible personnel will follow the standard procedures to ensure the protection of the blind within the Sponsor's clinical team. The randomization code or the individual analytical results will not be disclosed to any clinical team personnel prior to the database lock.

[figure not shown]
Refer to [Section 10.5](#) for suspected unexpected serious adverse reaction (SUSAR) unblinding by the Sponsor.

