Lexicon Pharmaceuticals Protocol No. EFC15166

Date of Issue: 21 November 2019
Covance Study ID: 000000155203

SAP version number	Date approved	Rationale	Description of statistical changes
2	05-Jun-2019	MedDRA version and dictionary updated	MedDRA version was updated to V22.0 and list of PTs for selected EOSI was updated
2	05-Jun-2019	Update categories of prior antidiabetic medication to cover all patients	Add "no antidiabetic therapy"
3	This version	Change in study Sponsor led to a strategic decision not to report the first step analysis in a standalone CSR	First step analyses will be combined with the second step analysis and both will be conducted at the end of the study in a single CSR The following sections/paragraphs are not applicable Section 2.4.4.4 – the last paragraph Section 3. – the first step analysis details Section 4. – the first data base lock
3	This version		
3	This version	Assess robustness of the ITT-based analyses	Identify possible need to conduct sensitivity analyses for PK anomalies
3	This version	Provide comparative analyses at Week 52 for the primary and secondary efficacy endpoints to further characterize the long-term effects of sotagliflozin	Apply statistical methods specified in Sections 1.6, 2.4.4.1, and 2.4.4.2 to the primary and secondary endpoints at Week 52
3	This version	Based on clinical guidelines for a higher A1C target for patients with chronic kidney disease.	Add another endpoint of proportion of patients with HbA1c <8%, at Week 26 and Week 52

* Change made in Protocol Amendment 1 dated 20-DEC-2017.

The first step analysis was conducted and reported for top line results; it was not used to inform a standalone Clinical Study Report (CSR) limited to just the 6-month data. A single CSR will be written for this study and will include the results coming from the analyses specified at both the first and second steps (see Section 3 of this SAP for more details).

The statistical methods detailed in this section will be performed in addition to those specified in other sections of the SAP. The majority of these additional assessments will serve as sensitivity analyses and will be used to support/qualify the robustness of results from the originally planned analyses.

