Patients in this study have undergone sampling for plasma levels of sotagliflozin and its main active metabolite in order to perform population PK analysis. Patients may be identified as those who have no detectable levels of active study drug or metabolite in their samples (ie, Below Limit of Quantification or BLOQ). When sample analysis has been completed and the study has been unblinded, explanations for some of these patients may be found: known non-compliance or sampling occurring after treatment had been discontinued. In other cases, drug intake history relative to the randomization assignment may not be fully explained. The ITT-based analyses specified in this document provides for a conservative assessment of the efficacy data should patients have been subjected to these unexplained non-compliance findings or PK 'anomalies'. To provide a broader perspective on the impact of these apparent errors in compliance, additional sensitivity analyses of the primary efficacy endpoint and continuous efficacy endpoints may be conducted. The need to perform such analyses, their specifics, and results will be provided in the Clinical Study Report (CSR), if applicable. The analysis methods applied to the patient subpopulations defined by the occurrence of the PK anomalies (eg, exclusion of patients with PK anomalies from the ITT dataset) will include the ANCOVA model using the retrieved dropout and/or washout MI methods, and the tipping point analyses previously specified in this section.

Analysis of the primary and secondary endpoints at Week 26 as specified in [Section 2.4.4.1](#) and [2.4.4.2](#) will be repeated for these same measures at Week 52, even though [Section 2.4.4.4](#) called for these analyses to be descriptive only. In addition, the sensitivity analysis methods described in this section will be applied to these variables at Week 52.

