2.1.5 Pharmacokinetic variables

Pharmacokinetic variables include the concentration of sotagliflozin and its 3-O-glucuronide metabolite in the sotagliflozin group (see study flowchart in [Appendix E](#) for designated visits).

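### The optional PK-based exclusion in SAP version 3 can flag only sotagliflozin patients, so agreement with it does not show that the ITT result is robust; the added Week 52 comparisons and HbA1c <8% need a label

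*SAP*

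**What the plan says.** SAP version 3 is dated 21 November 2019. The text after Table 2 in Section 1.6 states: "The first step analysis was conducted and reported for top line results". Three version 3 additions matter here.

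- **PK anomalies.** Section 1.6 describes patients whose samples show no detectable drug or metabolite. Some cases may be explained, namely "known non-compliance or sampling occurring after treatment had been discontinued"; others may not. Further sensitivity analyses may then be run, with "exclusion of patients with PK anomalies from the ITT dataset" as the example. The methods "will include the ANCOVA model using the retrieved dropout and/or washout MI methods", together with tipping point analyses. On the decision and the definition it says: "The need to perform such analyses, their specifics, and results will be provided in the Clinical Study Report (CSR), if applicable". Table 2 gives the rationale as "Assess robustness of the ITT-based analyses". Section 1.6 also calls the ITT analysis conservative.
- **Week 52.** Section 1.6 repeats the primary and secondary analyses at Week 52 and acknowledges that Section 2.4.4.4 had called for description only. Table 2 disapplies the last paragraph of 2.4.4.4. SAP 2.4.4, 2.4.4.3 and the second step in Section 3 still limit these results to description, as do Protocol 11.4.2 and 11.5.
- **HbA1c <8%** at Weeks 26 and 52 appears in Table 2 only.

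On which arms have PK data, SAP 2.1.5 defines the PK variables as "the concentration of sotagliflozin and its 3-O-glucuronide metabolite in the sotagliflozin group". Protocol 8.3.2 lets the bioanalytical laboratory use the randomization code "to allow for the sorting of the sotagliflozin plasma samples".

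**The concern.** A robustness check should ask whether the ITT conclusion survives a different but defensible handling of the same randomised comparison. This exclusion changes the comparison. An undetectable level is the expected finding on placebo, so a placebo patient who took no tablets cannot be flagged, while the equivalent sotagliflozin patient can be removed. Selection after randomisation then acts in the active arms only.

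The population is also undefined. The SAP does not say which or how many samples count, whether explained cases are removed, how dose interruptions are treated, or what happens to patients without a sample. These choices would be made after unblinding, with Week 26 results already known. Section 1.6 carries its sensitivity methods forward to Week 52, so the same open rule could recur there.

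At stake is what may be concluded: a CSR could cite agreement between this analysis and ITT as support that the analysis cannot give. For Week 52 and HbA1c <8% the stake is smaller: p-values outside the controlled family could be reported without saying so.

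**Working it through.** **The plan's own figure.** SAP 1.3 gives SD 1.2, difference 0.5, two-sided alpha 0.05 and 92 per group for 80% power. The formula 2(1.96 + 0.8416)² × 1.2² / 0.5² = 90.4 gives 91 per group. At 92 per group, power is 80.7% (normal) or 80.3% (t-test). The stated figure reproduces.

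**Model for the exclusion.** Effects are HbA1c points in favour of sotagliflozin. Let π be the share of an active arm that takes no drug and is excluded, τ the effect in takers, and Δ the amount by which non-takers would do worse than takers if both were untreated. By randomisation the placebo arm has the same mix of the two types, so:

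- ITT = (1 − π)τ
- Exclusion = τ + πΔ, because placebo keeps its non-takers
- Exclusion − ITT = π(τ + Δ)

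The documents give neither π nor Δ. I assume π of 5–20% and Δ of −0.5 to +0.5.

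**If the drug does not work (τ = 0).** ITT is 0 and the exclusion gives πΔ. The ITT SE is 1.2√(2/92) = 0.1769; the exclusion SE is 1.2√(1/92 + 1/(92(1 − π))). The chance of a favourable nominal result is 1 − Φ(1.96 − πΔ/SE), against 2.5% for ITT.

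| π | Shift, Δ = −0.5 to +0.5 | SE | Favourable result |
|---|---|---|---|
| 5% | −0.025 to +0.025 | 0.1792 | 1.8% to 3.4% |
| 10% | −0.05 to +0.05 | 0.1818 | 1.3% to 4.6% |
| 20% | −0.10 to +0.10 | 0.1877 | 0.6% to 7.7% |

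For example, at π = 20% and Δ = 0.5: 0.10/0.1877 = 0.533, and 1 − Φ(1.427) = 7.7%. A simulation of 40,000 trials at that point gave mean estimates of 0.000 (ITT) and 0.101 (exclusion), with favourable results in 2.7% and 7.9%.

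**If the drug works.** With ITT equal to the design effect of 0.5, τ is 0.526 at π = 5% and 0.625 at 20%. The exclusion then gives 0.50–0.55 and 0.53–0.73. With ITT of 0.25, τ is 0.263 and 0.313, and the exclusion gives 0.24–0.29 and 0.21–0.41. It falls below ITT only when Δ is below −τ, that is, when non-takers would have done better untreated by more than the drug effect.

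**Week 52.** Six measures (HbA1c, FPG, weight, UACR, <6.5%, <7%) at two doses make 12 tests; adding the two SBP measures makes 16. At 0.05 each, the expected number of nominal false positives under the global null is 0.6 or 0.8.

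**The case against.** The strongest reply is that the plan claims little. The PK analyses are optional, exclusion is only an example, ITT remains primary and is called conservative, and the stated aim includes a broader view of compliance errors. Late identification of cases also follows from blinding, because Protocol 8.3.2 withholds individual analytical results from the clinical team until database lock. All of this stands and limits the point. It does not answer the robustness rationale in Table 2, and the rule itself could have been written earlier.

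The sizes are also assumptions. The run-in requirement of at least 80% tablet compliance (Protocol 6.1.2) and drug accountability at on-treatment visits (Protocol 8.7.1) make 20% complete non-takers a high figure. The model gives every excluded patient no drug effect, whereas a patient sampled after discontinuation had taken drug.

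On Week 52, Section 1.6 openly overrides the descriptive-only rule. SAP 2.4.4.4 and Protocol 11.4.2.4 already leave these tests outside the controlled family, so a label and consistent text are all that is missing.

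Some SAP text is redacted. Section 1.6 refers to tipping point analyses specified earlier in that section, but none is visible there. This point covers the visible text, which expressly leaves the PK specifics to the CSR.

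Three stronger readings are not supported:

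- A reader might infer that exclusion would turn a near-miss into significance. With no prognosis gap, the expected exclusion estimate given an ITT estimate x is x + πτ. If τ = 0 it does not move and the SE grows: at π = 20%, an ITT p of 0.096 becomes about 0.117. A drop below 0.05 would be expected for such a p only if the true effect in takers were at least x/(1 − π).
- A reader might infer from the half-life that a two-week interruption would make a patient undetectable. The documents give quantification limits but no usual trough, so this cannot be judged.
- A reader might infer that the rule was shaped by the results. The documents do not show who wrote version 3 or whether PK data had been seen.

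**Conclusion.** The concern holds in limited form. The exclusion described in SAP 1.6 acts in one direction across arms, is defined after unblinding and estimates something other than ITT. Agreement with ITT therefore cannot be read as robustness. If the drug works, the exclusion will usually exceed ITT; if it does not, its direction depends only on the prognosis gap. Under the assumed 5–20% exclusion and gap of −0.5 to +0.5, the shift with no drug effect is at most 0.10 points either way. The confirmatory Week 26 ITT test and its alpha are untouched.

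The Week 52 and HbA1c <8% matter is minor: conflicting text and a missing label, with no familywise claim at risk. Section 1.6 also gives conflicting timing for the first step. Table 2 says both steps will be conducted at study end, while the text below it says the first has been done.

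**What to change.** **(a) PK exclusion.** Remove it as a robustness check. If a compliance analysis is wanted, use a rule that applies in all arms, such as the recorded dosing compliance in SAP 2.4.3.2; this removes the one-sidedness, though not the selection after randomisation. Otherwise, report the PK exclusion beside ITT as post hoc and exploratory, not as support for it. Its rule should be written and applied by staff blinded to outcome before the final lock, covering which samples count, explained cases, interruptions and patients without samples. Given Protocol 8.3.2, those staff would have to sit outside the clinical team. This cannot make the rule pre-specified for Week 26, because those results are already out.

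**(b) Week 52 and HbA1c <8%.** Align SAP 2.4.4, 2.4.4.3 and the second step in Section 3 with Section 1.6, and record the departure from Protocol 11.4.2 and 11.5. Label these comparisons as nominal, outside the 2.4.4.4 hierarchy and added after top-line. State that HbA1c <8% uses the responder method in SAP 2.4.4.2.

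**(c) Timing.** State which data cut gives the Week 26 result.

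The cost is SAP wording and one short definition, with no new data. Statements based on PK or Week 52 results become weaker.

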2 STATISTICAL AND ANALYTICAL PROCEDURES

2.1 ANALYSIS ENDPOINTS

2.1.1 Demographic and baseline characteristics

The baseline value (with the exception of serum creatinine and eGFR) is defined as the last available value before the first dose of double-blind IMP or the last available value prior to randomization for patients who were randomized but never exposed to IMP.

For serum creatinine and eGFR, the baseline value is defined as the average of all values before the first dose of double-blind IMP for those randomized and exposed or before randomization for those who were randomized but never exposed to IMP.

Baseline safety and efficacy parameters are presented along with the summary statistics for safety and efficacy sections ([Section 2.4.5](#) and [Section 2.4.4](#)).

Demographic characteristics

- Age (years) derived as: (Year of informed consent - Year of birth),
- Age categories (<50, ≥50 to <65, ≥65 to < 75, ≥75 years),
- Gender (Male, Female),
- Race (White, Black or African American, Asian, American Indian or Alaska native, Native Hawaiian or other pacific islander, Multiple, Unknown),
- Ethnicity (Hispanic or Latino, Not Hispanic or Latino, Unknown),
- HbA1c (%) at screening visit,
- Randomization strata of HbA1c (≤8.5%, >8.5%) at screening visit (data from IRT),
- Mean SBP at screening visit,
- Randomization strata of mean SBP (<130 mmHg, ≥130 mmHg) at screening visit (data from IRT),
- Baseline body mass index (BMI) (kg/m²) derived as: (Weight in kg)/(Height in meters)²,
- Baseline BMI categories (<30, ≥30 kg/m²),
- Country.

Disease characteristics at screening or baseline

Disease history includes:

Duration of diabetes (years) derived as: (Date of informed consent – Date of diagnosis of Diabetes + 1)/365.25,

- Duration of diabetes categories: (<10, ≥10 years),
- Age at diagnosis of diabetes (years) derived as: Year of diagnosis of diabetes – Year of birth,
- Prior use of sodium-glucose cotransporter type 2 (SGLT2) (Yes, No),
 - Prior antidiabetic medication (no antidiabetic therapy, insulin, non-insulin),
- Baseline diabetic microvascular complications (Yes, No) [ie, diabetic retinopathy, diabetic neuropathy, diabetic nephropathy (duration of diabetic nephropathy for patients with diabetic nephropathy), diabetic peripheral neuropathy (sensory or motor), diabetic autonomic neuropathy, and diabetic foot infection],
- Baseline UACR categories (<30 mg/g [Normal], ≥30 to <300 mg/g [Microalbuminuria], and ≥300 mg/g [Macroalbuminuria]),
- eGFR at screening (mL/min/1.73m²),
- Prior antihypertensive medication identified by therapeutic class as agents acting on the renin-angiotensin system, beta blocking agents, diuretics (a sub-category: loop diuretics identified by pharmacological class as high-ceiling diuretics), calcium channel blockers, and antihypertensives according to World Health Organization-Drug Dictionary (WHO-DD).

Medical or surgical history

Medical history and medical findings include:

- Physical examination,
- Medical or surgical history,
- Medical history cardiovascular,
- Surgical history amputation,
- Alcohol habits,
- Tobacco smoking habits.

Medical and surgical history will be coded to a “lower level term (LLT)”, “preferred term (PT)”, “high level term (HLT)”, “high level group term (HLGT)”, and associated primary “system organ class (SOC)” using the version of Medical Dictionary for Regulatory Activities (MedDRA) currently in effect at Sanofi at the time of database lock.

Any technical details related to computation, dates, and imputations for missing dates are described in [Section 2.5](#).

2.1.2 Prior or concomitant medications

All medications taken in the 3 months before the screening visit (any time for prior SGLT2) until the end of the study are to be reported in the electronic case report form (e-CRF).

All medications will be coded using the World Health Organization-Drug Dictionary (WHO-DD) using the version currently in effect at Sanofi at the time of database lock.

- **Prior medications** are those the patient used prior to first administration of double-blind IMP. Prior medications can be discontinued before first administration or can be ongoing during treatment phase.
- **Concomitant medications** are any treatments received by the patient concomitantly to the IMP, from the 1st administration of double-blind IMP to the date of last administration + 15 days. A given medication can be classified both as a prior medication and as a concomitant medication. **Posttreatment medications** are those the patient took in the period running from the 16th day after the last administration of double-blind IMP up to the end of the study.

Any technical details related to computation, dates, imputation for missing dates are described in [Section 2.5](#).

2.1.2.1 Rescue therapy

Open label rescue medication(s) to treat hyperglycemia must be in accordance with local standard of care and prescribing practice for patients with CKD and will be at the discretion of the Investigator. Except for SGLT2 inhibitors and medications with specific contraindications in renal impairment, any approved medication(s) including oral antidiabetic drugs or insulin can be considered with appropriate dose modification as indicated. Rescue therapy is considered as a noninvestigational medicinal product (NIMP).

2.1.2.2 Prohibited prior and concomitant medications

During the study treatment period, the following medications are prohibited:

- Initiation of any antidiabetic agents, including oral or injectable antihyperglycemic agents other than the IMP and NIMP is not allowed before the rescue therapy. The existing background medication (NIMP) should not be modified before the rescue.

Note: short term use (<10 consecutive days) of the prohibited medication eg, short-acting insulin for treatment of acute illness or surgery is allowed.

- SGLT2 inhibitors (eg, canagliflozin, dapagliflozin, or empagliflozin) are not allowed for rescue.
- Systemic use of glucocorticoids for more than 10 consecutive days (topical, intra-articular, ophthalmic, nasal spray or inhaled applications are allowed).
- Investigational medicinal products in any other clinical study.
- Modification of antihypertensive medication before Week 12 is not allowed unless for safety reasons.
- Initiation of any weight loss drugs (eg, phentermine, orlistat).

- Reduction of digoxin dose should be considered because sotagliflozin acts as a weak P-glycoprotein (P-gp) inhibitor and increases systemic exposure to digoxin.

Patients taking sotagliflozin with concomitant digoxin should have digoxin concentrations monitored and doses reduced as needed. In addition, other P-gp substrates may be affected and the labels of P-gp substrate drugs should be consulted with regards to monitoring and dose adjustments.

Other medications which are unlikely to interfere with the pharmacokinetic (PK) or pharmacodynamics (PD) of the IMP or confound interpretation of the study endpoints are allowed as needed following discussion between the Investigator and the Sponsor/CRO. However, doses of chronically administered medicines should be kept fixed during the trial if at all possible.

The dose of all antihypertensive agents should be kept constant during the 12 weeks following randomization and no antihypertensive agents should be added or withdrawn for the 12 weeks following randomization unless it is considered necessary for safety reasons.

2.1.3 Efficacy endpoints

All efficacy measurements collected during the study will be considered for analyses, including those obtained after IMP discontinuation or introduction of rescue therapy (see [Section 2.5.4](#)).

HbA1c, FPG, UACR, UGE, urine glucose: creatinine ratio (UGCR), Cystatin C, Fructosamine, NT-proBNP and eGFR are measured/calculated in a central laboratory (see study flowchart in [Appendix E](#)). FPG, Cystatin C, Fructosamine, NT-proBNP are measured in the fasting state. Body weight, SBP and DBP (see [Section 2.1.4.5](#)) are measured at on-site visits by the investigator. Patients requiring rescue are identified as those with the reason for treatment ticked “rescue therapy” in e-CRF “Medication” page.

Efficacy variables will be summarized in both standard international units and conventional units when applicable.

2.1.3.1 Primary efficacy endpoint(s)

Change from Baseline to Week 26 in HbA1c (%) comparing sotagliflozin 400 mg versus placebo in CKD stage 4 patients.

